## **15. RISK MANAGEMENT PROCEDURES AND ADEQUACY OF RESOURCES**

In addition to the protections against risks briefly outlined in the Potential Risks section above, additional precautions have been outlined to reduce risk for violence to wives, given the vulnerability of this population. These protocols and procedures were developed based on WHO guidelines for domestic violence research, and based on existing NIH-funded projects Drs. [name] and [name] have or have had in both India and the US. These protocols include (but are not limited to) the following efforts:

If women at any point in the study report life-threatening violence from husbands, these women will be withdrawn from the study and provided with supported referral (assistance with transport and accompaniment) to a state domestic violence agency (CEHAT) by research or program staff. Research staff, ANMs, and trained providers/counselors will be trained on how to work with women in these situations in accordance with WHO guidelines for domestic violence research. For example, this includes using "dummy" questions if privacy is breached during an interview or an ANM or trained provider/counselor visit, and training staff to identify when women are distressed and need debriefing or immediate health attendance. They will also offer support to conduct a safety plan with woman reporting spousal violence to ensure she has thought through ways to safely escape her situation should she choose to do so.

Research and program staff will never disclose to any family member who participated in the study, what questions were asked of them, or what responses were given. Participants will also be asked not to share the questions and their responses with others, particularly if they think it could put them at risk for abuse. This is in line with WHO procedures for domestic violence research.

Women will always be assessed for domestic violence in private places, with clarification that women can refuse to respond to items or questions, with supported referral and safety planning for identified victims, with validation that violence is never a woman's fault, with protocols and confirmation that all information provided is kept confidential, and with emotional debriefing subsequent to disclosure, in line with WHO procedures for domestic violence research.

Participation in this study and programs is completely voluntary. If the participant feels uncomfortable or is upset by the interviews or surveys or intervention sessions, she/he may withdraw from the study as outlined by the consent form.

Only wives will be assessed for marital violence in the surveys and intervention sessions; they will be asked not to disclose participation in these items as it may put themselves or others at risk for violence as a consequence of study participation. Utmost confidentiality will be maintained by all research staff. Please see section below on "Protection from Loss of Confidentiality" for details. These protocols to protect women's confidentiality are in line with WHO guidelines on domestic violence research.

It must be noted that there is no law against marital sexual violence/rape in India at this time. [name] works closely with many groups in India that work on issues of domestic and sexual violence, including Amnesty International India and CEHAT, allowing this team to be abreast of the most up to date laws and services to support victims who are identified and wish to seek services. Our experience from the original CHARM study as well as other studies is that women rarely wish to obtain formal support against domestic violence.

**Protection from Loss of Confidentiality:** As noted in the section on Potential Risks, security of confidentiality is a primary means of reducing risks for our research participants. Hence, every effort will be made to minimize participants' risk of a loss of confidentiality during this study. Participants will not have family members or others informed of their participation in the study unless they choose to tell them. Participants from the same household or institution will not be informed of the survey questions or responses for other members of their household or institution, or the nature of the interventions offered. Only unique identifiers will be used to label data collected in this study; only NIRRH staff and Co-Is will have access to the identifiable information linked with the unique identifiers. These research staff will be required to maintain the confidentiality of all research participants, and will have signed a pledge to do so upon joining the research team.

All participants will be informed, via written informed consent that any disclosure requiring our mandated reporting (e.g., perpetration of homicide, child abuse, or elder abuse; suicidality; homicidal intentions) will require that we contact authorities and provide them with identifiable information about the participant if we have it. We will also immediately escort them to mental health services care available at the community health center if they disclose that they are suicidal or homicidal; that may result in them involuntarily being made an inpatient in a psychiatric facility. If the participant informs us of abuse of children (exclusive of minor aged wives) or elders or perpetration of homicide, the authorities will also be contacted. This will be outlined in the informed consent. No procedures included in this study will involve assessment of any of the above concerns except suicidality.

**Protections for Research Staff:** The research and program staff will be trained not to provide judgment regarding participants' sexual behavior, parity, marital age or circumstances, victimization from violence, substance use or other stigmatized behaviors; as described above, all participants will receive referrals for relevant health and social services related to family planning and, for wives only, domestic violence programs. Standard provision of referrals to all participants, and clarity via consent forms regarding this standard provision, allows us to safely offer information without increasing our staff's vulnerability. To further help protect staff, both program and research staff will be trained in security protocols regarding how to reach nearby police or other staff members on short notice, if an issue becomes apparent; all staff will have cell phones to make such contact. Participants will be given the NIRRH PI's name and work phone number on the consent materials. Research and program staff will be trained on how to stay alert to participant distress and signs that the participant is becoming irritated by the questions or discussion. In addition to providing support and information to participants as described above, all research staff will be trained to end the participant's involvement if they (the staff) have any concerns for their own safety. If a situation of mandated reporting arises, research staff will be well trained to manage the situation. They will first contact the authorities to inform them of a potential security issue; this contact will be made in a way that does not alert the participant that the authorities have been contacted. Once the authorities arrive, the staff member will inform the participant that a mandated reporting issue has arisen, identify the issue for the participant, and remind the participant that this requires study termination and that authorities be contacted. All staff will be trained in these procedures by [name], an expert on violence and ethics in research, as well as Drs. [name] and [name], who have expertise conducting sexual and reproductive health research in India.

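### The covert-contact sequence for mandated reporting makes no exception for a suicidal participant, so staff who follow it literally could delay the immediate escort to care that the same section requires

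*Combined protocol and SAP*

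**What the plan says.** Two parts of Section 15 direct what staff do after a suicidal disclosure.

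The first is the text on protection from loss of confidentiality. Participants are told at consent that authorities will be contacted about "any disclosure requiring our mandated reporting (e.g., perpetration of homicide, child abuse, or elder abuse; suicidality; homicidal intentions". For two of these disclosures it adds a care step: staff will also "immediately escort them to mental health services care available at the community health center if they disclose that they are suicidal or homicidal". Abuse and past homicide are handled in a separate sentence, which opens "If the participant informs us of abuse of children (exclusive of minor aged wives) or elders or perpetration of homicide" and provides for contact with authorities but no escort.

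The second is the paragraph on protections for research staff. Its trigger is general: "If a situation of mandated reporting arises, research staff will be well trained to manage the situation". The sequence that follows opens with "They will first contact the authorities to inform them of a potential security issue". The call is to be kept from the participant, for whom the paragraph specifies that "this contact will be made in a way that does not alert the participant that the authorities have been contacted". The explanation is the later step: "Once the authorities arrive, the staff member will inform the participant that a mandated reporting issue has arisen". The participant is also reminded that study participation ends. The paragraph separately lets staff end a participant's involvement if they fear for their own safety.

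Three other places bear on the point:
- Section 14 provides for an immediate escort to a mental health provider when a distressed participant needs help at once. It introduces this by noting that a participant might become a risk to self or others.
- Section 18 repeats that risk and says such people will be linked to care immediately.
- Section 16 says that for suicidal intent the researcher contacts authorities at once. It allows these to be police or mental health services, and it mentions no escort.

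**The concern.** A covert call to authorities, with the explanation held back until they arrive, suits a threat to staff or a disclosed crime. It suits a suicidal participant poorly, because the useful response there is prompt, open accompaniment to care. Yet the trigger for the sequence is any mandated-reporting situation, and Section 15 itself places suicidality in that category.

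The situation is foreseeable. Section 14 says such disclosures could arise in an intervention session or in the debriefing after the survey. Section 15 adds "No procedures included in this study will involve assessment of any of the above concerns except suicidality". Section 16 says these matters are not directly asked about, but a disclosure can occur either way.

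Survey assessments take place in participants' homes in rural Maharashtra (Sections 3 and 9), and the documents give no response time for authorities. What is at stake is that a suicidal participant might be kept waiting for authorities called to a security issue when Section 15 intends an immediate escort. This is a matter of participant safety, not of statistical design.

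**Working it through.** There is no planned figure to reproduce. The check is a comparison of texts.

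1. **Is suicidality inside the trigger?** Yes. The Section 15 list names five examples: perpetration of homicide, child abuse, elder abuse, suicidality and homicidal intentions. The staff-protection sequence applies to a situation of mandated reporting and excludes none of them.

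2. **What does the care clause require?** An escort, immediately, for a participant who is suicidal or homicidal. The word *also* makes it additional to contacting authorities, so it does not replace that contact.

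3. **What does the sequence require, and in what order?** Contact authorities first; conceal the contact; explain when they arrive; end participation. It contains no escort step and does not say where one would fit.

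4. **Coverage by count.**
   - Sequence: 5 of 5 listed disclosures, 0 exceptions, 0 mentions of an escort.
   - Escort clause: 2 of 5 (suicidality, homicidal intent).
   - So for 2 of 5 both rules apply, and the text does not say how they fit together.

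5. **Can both be obeyed?** Yes. A staff member could make a discreet call and then escort the participant, and nothing in the sequence forbids this. The difficulty is timing. Escorting someone to mental health care realistically means telling them where they are going and why, and the sequence places the explanation after the authorities arrive. Someone following it step by step would probably wait.

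6. **Do other sections settle the order?** Sections 14 and 18 reinforce immediate care for a person at risk to self, and Section 14 names an escort. Section 16 widens who the authorities may be. None of them says that the escort takes precedence over the covert sequence.

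7. **Can the delay be sized?** No. The documents give neither a response time nor an event rate. Section 14 reports that similar earlier work elicited no such responses, so events should be rare.

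**The case against.** The best case on the other side is that this is a missing cross-reference inside one section. The staff-protection paragraph exists for security, as its heading and its first step show. Participant care is set out elsewhere, in specific and urgent terms. A sensible reader would not let a staff-safety paragraph override an explicit instruction to escort at once.

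Several facts also soften the harm scenario. Section 16 lets the authority be a mental health service. Staff carry cell phones and are trained to reach police or colleagues quickly. Section 11 describes two-person teams for screening and recruitment. All staff are to be trained in these procedures, and the training materials are not among the documents, so what staff will actually be taught is unknown.

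Much of this stands. A reader might infer that Section 15 contradicts itself; it does not, because both instructions can be carried out. A reader might also infer that the escort is an isolated promise, or that the plan leaves a suicidal participant without care. Sections 14 and 18 show otherwise.

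What does not fall away is the general trigger. The heading explains the paragraph's purpose but does not limit when its sequence applies. That sequence is the only step-by-step procedure the plan gives for mandated reporting, and it is the one staff are to be trained in. Allowing the authority to be a mental health service still leaves the timing of the escort unstated.

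**Conclusion.** The point holds as an unreconciled order of steps. The sequence includes suicidality without exception, and literal use of it could delay the immediate escort. It is a minor participant-safety correction that is cheap to make. It has no effect on power, endpoints or the analysis.

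The conclusion rests on two assumptions: that field staff would treat the sequence as written, and that an escort realistically needs some explanation to the participant beforehand. It does not rest on any estimate of how often this would happen or how long a delay would be, since the documents support neither. The consent pages were not available, so nothing is claimed about them.

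**What to change.** In the staff-protection paragraph of Section 15:

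- State that for a suicidal disclosure the immediate escort to mental health care governs. Any required notification, which Section 16 allows to be to mental health services, is made alongside the escort and must not delay it. The existing rule that staff may stop if they fear for their own safety continues to apply.
- Limit the covert-contact sequence to homicide, homicidal intent, reportable abuse and staff-security situations.

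Two existing protections should be left untouched. One is the carve-out for minor-aged wives in the abuse-reporting sentence. The other is the handling of spousal violence through confidentiality, supported referral and safety planning, which this change should not turn into reports to authorities.

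The cost is two or three sentences, delivered through training that is already planned. Accompaniment is not a new kind of task, since Section 15 already has staff accompany women to a domestic violence agency. The downside is that staff lose one uniform rule and must distinguish suicidality from the other disclosures. No extra visits, staff or participants are needed.

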### **Importance of the Knowledge to be Gained**

Data collected from this project will be used to create program efforts that can be integrated into national rural health and family planning policies and initiatives, with the goal of improving family planning and reducing unintended pregnancy at a population level.

**Interim Safety and Efficacy Review.** Study risks are low. However, we will convene a Data and Safety Monitoring Board (DSMB) to review safety on a yearly basis. The study will be stopped early if there are serious safety concerns or early evidence of a large beneficial treatment effect. An interim efficacy analysis will be conducted after half of subjects (n=10 geographical clusters) have completed the 18 month visit. The O'Brien-Fleming stopping rule for efficacy will be used. Because validation of the proposed CHARM2 intervention is scientifically important independent of statistically significant results, there will be no futility analysis. The DSMB will consist of experts on FP, MSV and clinical trials in India.

**Confidentiality and Security.** Data security and confidentiality are critically important due to the sensitive subject matter of this study. All participant identifiers such as name, address or telephone number will be maintained on separate forms in locked storage at NIRRH and kept separately from the analytic database. Data shared among NIRRH, Population Council, and UCSD will be maintained on password-protected and secure servers at each site. The data will be backed up nightly on the UCSD server.

### **Data and Safety Monitoring Plan.** Data safety monitoring of study participants will focus on two major safety aspects:

1. assurance that no harm comes to participants as a result of survey or program participation and
2. assurance that all data collected from this project, including process and quality assurance data as well as outcome data, maintain the privacy of research participants. [name] will oversee project staff to ensure that the data safety monitoring plan is being properly adhered to within India.

Measures to ensure that no harm comes to participants as a result of survey participation are described above under the sections on Potential Risks and Protections against Risks

In terms of data management, all hard data (e.g., paper surveys if a tablet malfunctions in the field) collected from this study will be brought to the lead field site (NIRRH) for transcription and translation; tapes will be locked away until transcription and then destroyed. Electronic files created from this transcription/translation will be compiled and analyzed at NIRRH. Hard data safety will be assured by locking the consent forms, contact numbers and addresses in separate securely locked cabinets in a locked office that is only accessible to NIRRH. All research staff who collect and have access to data from this study will sign a certificate in which they agree to maintain absolute confidentiality of all participants within this research project. If any security arrangement is violated, either through physical tampering or breach of confidentiality, the individual making the discovery will notify the Principal Investigators and the NIRRH and UCSD IRBs. Data analysis will occur at UCSD; electronic files will be kept on a password protected project drive within the school's network. Access to this data will only be made available to investigators and research staff from the project; the data will be password protected. Data files at UCSD are backed up nightly to minimize the likelihood of lost files.

This study has moderate risk. The risks are reasonable in relation to benefits/knowledge gained. Serious risk is unlikely. Major risk is attached to the study's focus on sensitive topics such as family planning and sexual violence. As noted, a number of efforts have been undertaken to reduce risks for study participants. In addition, we have developed both internal and external data safety and monitoring procedures, and a plan to determine if halting of study procedures are required. These are as follows:

## **16. PRIVACY AND CONFIDENTIALITY CONSIDERATIONS INCLUDING DATA ACCESS AND MANAGEMENT**

Every effort will be made to minimize participants' risk of a loss of confidentiality given the sensitive issues covered by this study. Research staff and village health providers will be required to maintain confidentiality of all research participants, and will have signed

a pledge to do so upon joining the research team. All data collected from this study will be identified only by the unique identifier, so it will be difficult to trace an individual's participation or study data in this project without the unique identifier list linked with identifier information, and that list that will be kept under lock and key at NIRRH. Further, data transmitted to the larger team will be de-identified or labeled only with the unique identifier, to reduce risk for breach of confidentiality in transference of data for this international research study. All NIRRH staff with access to identifiable information will sign a confidentiality agreement to ensure they maintain the confidentiality of all study subjects; if there is any indication of a breach of this confidentiality, [name] will take immediate efforts to identify the breach and terminate employment of anyone directly causing it.

There are some circumstances in which confidentiality will be breached by the researchers. If the participant directly informs a researcher of his/her perpetration of abuse against children (those under age 18 years) or elders (those 65 years or older), or his/her intentions of homicide or suicide, the researcher will immediately contact authorities (police or mental health) to help address the issue. However, as part of informed consent we will let all participants know this, and we do not directly assess any of these questions via our data collection processes. These procedures have been used in the past on diverse projects within India conducted by Drs. [name] and [name], and there have been no issues that have arisen.

## **17. POTENTIAL BENEFITS**

All study participants will receive referrals to or information regarding local health and social service programs, including family planning services and domestic violence program referrals, of which they may have otherwise been unaware. They are also provided with information and skills to approach their marital relationships in a more gender-equitable way. Furthermore, awareness and linkage to family planning services and domestic violence programs may improve their sexual and reproductive outcomes. Given that the potential benefits of the study would allow for the development of an intervention to improve maternal health and child survival and that there are multiple mechanisms in place to manage potential risks from study and intervention involvement, we believe the benefits outweigh the risks for this proposed study.

## **18. RISK/BENEFIT RATIO**

The potential risks for male and female participants may be different. Questions asked in the interviews and surveys to men may be embarrassing as they assess their gender ideologies, attitudes and norms about reproductive choices and contraceptive use, while the questions asked to women may be embarrassing and upsetting as they assess husbands' gender ideologies and abusive or controlling behaviors, her knowledge and intentions about fertility and contraceptive behavior. Embarrassment among both male and female participants is reduced by the brevity of the research tools and the use of trained, gender-matched interviewers or demographers. Nonetheless, it is possible that some participants may become anxious, depressed, or angry due to this content, and there is a small possibility this may result in their becoming a risk to themselves or someone else. Efforts will be made to link those to care immediately if such concerns arise. Our previous work in India using similar items (including items of abuse, substance use and sexual infidelity) and a similar approach (e.g., one-on-one rather than couple survey implementation) has elicited no such responses. An additional risk in the pilot and efficacy phases is related to reactions to pregnancy test results; some could be upset by positive test results. To maintain optimal safety for wives, we will only inform wives of the test results in this study. They will then have the option of reporting those results accurately, inaccurately or at all to their husbands. Interviewers will not dispute women's reports, and marking of the test result will be conducted in a way that cannot be assessed by participants. Additionally, all women will be provided with verbal referrals for ASHAs (village women's health outreach workers) and the closest Primary Health Center (a facility which provides antenatal and family planning services), regardless of these test results.

With recognition of the high rates of male-perpetrated partner violence among young couples in rural India, special efforts will be made to prevent study involvement from inciting violence against wives. We will only include couples in which wives are allowed to participate and to participate in accordance with study design (private survey administration with wives). Male abuse and control behaviors will only be asked of wives and men will not be informed that wives will be assessed on these items; wives will be asked not to disclose survey questions and their responses to their husbands unless they feel very safe. The informed consent of the men serves as an agreement that the information researchers obtain from both men and their wives will remain confidential and would not be shared between investigators as well as between participants. In addition, the survey tools will be piloted to understand their sensitivity administering to both men and their wives; if any issues are identified, items will be revised or dropped accordingly. Notably, survey items and procedures proposed are similar to those used in the NFHS-3 and previous couples research from Drs. [name] and [name]; these efforts assessed partner violence in couples and no adverse outcomes were observed. This approach also follows WHO guidelines for Domestic Violence research. To provide greater support for participants, both husbands and wives in each phase of study will receive referrals to health workers known for having good sensitivity on issues of partner violence and family planning options. If, despite all these precautions, we find that there is a violence happening as a result of study participation, we will make efforts to stop through the use of local village committees and health care workers. If we see an inability to stop the violence even after our efforts, a highly unlikely scenario, the study will be terminated. Identification of such issues will be noted as adverse events and reported accordingly to all investigators, NIRRH, UCSD, Population Council.

Based on the above rationale and the knowledge that is expected to result from this study to inform intervention practices and policy implications around family planning approaches in rural India, and our belief that the risks associated with this study are minimal in relation to the possible benefits to the broader community, we feel that there is an appropriate risk/benefit ratio for this study.

